7.3 RECORDS RETENTION17

8 STUDY FINANCES 18

8.1 FUNDING SOURCE 18
8.2 CONFLICT OF INTEREST 18
8.3 SUBJECT STIPENDS OR PAYMENTS 18
8.4 REGULATORY INFORMATION 18
9 REFERENCES 19

LIST OF ABBREVIATIONS

AE	Adverse Event/Adverse Experience
HIPAA	Health Insurance Portability and Accountability Act
PTT	Penile traction therapy
PD	Peyronie's Disease
RCT	Randomized controlled trial

Study Summary

Title	Penile Lengthening Maintenance Post-prostatectomy
IRB Protocol Number	18-001013
Methodology	Controlled randomized study
Overall Study Duration	3 years
Subject Participation Duration	9 months
Objectives	Evaluate the efficacy of the RestoreX penile traction device in preventing loss of penile length in men undergoing prostatectomy
Number of Subjects	90
Diagnosis and Main Inclusion Criteria	Men undergoing prostatectomy
Study Device	RestoreX®, penile traction therapy
Duration of Exposure	Subjects will use device for 5 months for: 30 minutes, once daily, 5 days a week OR 30 minutes, twice daily, 7 days a week After the randomized period, all subjects will be entered into an open-label phase where they may choose to use or not use the device for 3 additional months
Reference therapy	During the randomized phase, the use of the device will be compared against a control group using no traction therapy In the open label phase, results at the end of 9 months will be compared to those from baseline and at the beginning of the open label phase
Statistical Methodology	Stratification of subjects prior to randomization to assure an equal representation based on baseline penile length. Statistical comparisons will be made comparing total penile length prior to and following therapy. Comparisons of subjective questionnaire responses will also be made between groups and at the various time points captured.

1 Introduction

This document is a protocol for a human research device study. This study will be carried out in accordance with the procedures described in this protocol, applicable United States government regulations and Mayo Clinic policies and procedures.

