1.1 Background

The treatment of prostate cancer results in several known sexual dysfunctions, including erectile dysfunction, orgasmic dysfunction, ejaculatory dysfunction, penile curvature (Peyronie's disease), and reduced penile length. Although all forms of prostate cancer treatment are associated with many of these changes, prostatectomy currently has the most data available on sexual function outcomes. Among the dysfunctions, loss of penile length is often one that results in significant distress and bother to patients. Beyond the esthetic concerns, reduced penile length may lead to inability to participate in sexual intercourse, difficulty with future interventions to restore erectile function (placement of a penile prosthesis), and lead to worsened urinary hygiene (leak urine onto self, leading to yeast infections and other issues).

Penile traction therapy (PTT) is currently the best available treatment to maintain or restore lost penile length due to conditions that reduce length.¹ Prior studies evaluating penile length maintenance post-prostatectomy have utilized a vacuum erection device with varying rates of efficacy. However, to date, no studies have evaluated the benefits of using PTT in this clinical setting. The objective of the current study is to evaluate the efficacy of a novel, Mayo-clinic developed PTT device in maintaining (randomized phase) or restoring (open label phase) reduced penile length.

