2.2 Secondary Objectives

1. Compare patient compliance with traction device.
2. Compare patient reported satisfaction with use of traction device.
3. Evaluate any adverse events (AEs) with use of RestoreX® for penile lengthening.
4. Compare the rate of Peyronie's disease development among groups
5. Compare patient satisfaction scores including satisfaction with overall penile length.
6. Evaluate and compare patient erectile function among groups
7. Compare penile length outcomes pre- and post-open phase traction therapy
8. Evaluate the duration of treatment utilized during the open phase of treatment
9. Review associations between pre-surgical factors (demographics, disease-specific factors, and standardized questionnaires) and outcomes

3 Study Design

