3.5 Study Schema

Prior to surgery, data will be recorded by the surgeon using the current standard of care questionnaires (EPIC-50, IIEF-15 disease specific variables, and demographics).

Following surgery, patients will be seen in the clinic based on the standard routine clinical practice for their catheter removal (approximately 1-3 weeks post-prostatectomy). At this time, and after the patient has consented, they will undergo initial study penile length assessments (described later in the protocol) and be educated on how to use the device properly by a trained nurse. Patients will then be given a baseline questionnaire to complete. In some cases, patients may not have been provided the IIEF-15 questionnaire prior to surgery. For these patients that have not yet filled out this questionnaire and had their data recorded in their records, they will instead receive the IIEF-15 questionnaire during this baseline visit.

Once consent and study assessments are completed, the patients will be randomized into one of three groups:

1. PTT for 30 min 1x/day, 5 days/week
2. PTT for 30 min 2x/day, 7 days/week
3. Control (no treatment)

Patients in the treatment arm will record a daily journal of their usage of the device. Patients will then begin using the device 4 weeks after surgery as instructed for the times appropriate to their group. This ensures adequate time for the patient to recover from their procedure before beginning to use the device. The study coordinator will call the patient to remind them to begin using the device.

After 5 months of using the device (+1.5 months permitted), patients will return for subsequent assessments (see below) and a follow-up questionnaire. At this time, patients will be encouraged to report any adverse events. They will also be requested to bring their device back to the clinic to review proper usage and any questions on the device. After completion of the subsequent assessments, patients will begin a 3-month, open-label phase of the trial. During this period, the patients will be allowed to use the device for 30 minutes at a time, with a frequency to be determined by the patient.

After completion of the 3-month open-phase portion of the trial, patients will return to the clinic to undergo final assessments, which are identical to the 6-month assessments. Patients will then be encouraged to self-report any additional adverse events (AE's) that they encounter over the subsequent 6 months.

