5.2 Statistical Analysis

Analyses will be performed using comparisons within patients of same baseline penile stretch length and between groupings of varying lengths. Comparison of penile length between traction and no traction will be made, as well as reviewing historical records to increase statistical power. Comparison of length from baseline to post-traction for individual participants will also be reviewed.

The data will also be analyzed in three ways: 1- with all patients included, regardless of their compliance to utilize the device for the recommended treatment time, 2- with patients excluded if they failed to achieve 90% compliance with the recommended duration of treatment, 3- with patients excluded if they failed to achieve 80% compliance with the recommended duration of treatment.

Comparisons will also be made on other subjective and objective variables obtained including number of adverse events, complications, subjective responses to questionnaires, or

other information. All data will be normalized based on pre-operative stretched penile length.

6 Safety and Adverse Events

Definition of Adverse Event

Unanticipated Problems Involving Risk to Subjects or Others (UPIRTSO) - any unanticipated problem or adverse event that meets the following three criteria:

Serious: Serious problems or events that results in significant harm, (which may be physical, psychological, financial, social, economic, or legal) or increased risk for the subject or others (including individuals who are not research subjects). These include: (1) death; (2) life threatening adverse experience; (3) hospitalization - inpatient, new, or prolonged; (4) disability/incapacity - persistent or significant; (5) breach of confidentiality and (6) other problems, events, or new information (i.e. publications, interim findings, product labeling change) that in the opinion of the local investigator may adversely affect the rights, safety, or welfare of the subjects or others, or substantially compromise the research data, AND

Unanticipated: (i.e. unexpected) problems or events are those that are not already described as potential risks in the protocol, consent document, not listed in the Investigator's Brochure, or not part of an underlying disease. A problem or event is "unanticipated" when it was unforeseeable at the time of its occurrence. A problem or event is "unanticipated" when it occurs at an increased frequency or at an increased severity than expected, AND

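### The only length analyses named for the open-label phase are uncontrolled before-after comparisons, which cannot by themselves support the restoring aim; a 9-month comparison by randomised arm should be added as an early-versus-delayed analysis

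*Combined protocol and SAP*

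**What the plan says.** Section 1.1 divides the efficacy question between the two phases: the device is to be evaluated "in maintaining (randomized phase) or restoring (open label phase) reduced penile length".

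Two places name a length analysis for the open-label phase, and both are within-participant. The Study Summary (Reference therapy) says that "results at the end of 9 months will be compared to those from baseline and at the beginning of the open label phase". Secondary objective 7 (section 2.2) is "Compare penile length outcomes pre- and post-open phase traction therapy".

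Use in this phase is voluntary in all three arms. The Study Summary (Duration of Exposure) says "they may choose to use or not use the device for 3 additional months", and section 3.5 allows 30-minute sessions "with a frequency to be determined by the patient".

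Section 5.2 adds two general statements, neither tied to a visit: "Comparison of penile length between traction and no traction will be made" and "Comparison of length from baseline to post-traction for individual participants will also be reviewed". The Study Summary mentions between-group comparisons at the different time points only for questionnaire responses. Length is scheduled at baseline, 6 months and 9 months without restriction by arm (sections 4.2 to 4.6).

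**The concern.** The randomised phase has a no-treatment control because length may change after prostatectomy whatever is done. The open-label analyses drop that control. A change from month 6 to month 9 mixes any device effect with natural change over the same months. Relating that change to hours of use does not repair this, because the men who use the device more have chosen to do so.

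The 9-month versus baseline contrast isolates the phase even less well. Baseline is at catheter removal, about 1 to 3 weeks after surgery, so in the two traction arms the contrast also contains the 5 months of randomised treatment. In the control arm it contains the whole untreated interval up to the 6-month visit.

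At stake is whether a significant before-after change could be read as restoration by the device. A question that the randomisation can address is also left unstated: does a difference between arms at 6 months persist once controls may use the device?

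**Working it through.** **1. What is specified.** Four candidate statements could supply a controlled 9-month length comparison.

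- Study Summary, Reference therapy: 9 months against baseline and against the start of the phase. No comparator arm.
- Section 2.2, objective 7: before against after the open phase. No comparator arm.
- Section 5.2, traction against no traction: no time point. At 9 months no arm has been held untreated, so this does not define a 9-month contrast.
- Section 5.2, baseline to post-traction: within-participant.

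No place names 9-month length by randomised arm.

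**2. The plan's own figure.** Section 3.4 gives 30 men in each of three arms, and 3 × 30 = 90. The documents give no alpha, power, effect size, SD or dropout rate, so 90 cannot be reproduced as a power calculation. Everything below therefore rests on stated assumptions.

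**3. Before-after comparison with zero device effect.** Assume a natural 6-to-9-month gain of d SDs of the change score, a paired t test at two-sided 0.05, and no missing lengths. The chance of a significant gain is P(T > t₀.₉₇₅,ₙ₋₁), where T is noncentral t with n − 1 degrees of freedom and noncentrality d√n. The critical value is 2.045 for n = 30 and 1.987 for n = 90.

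| d (assumed) | d√30 | n = 30 | d√90 | n = 90 |
|---|---|---|---|---|
| 0 | 0 | 2.5% | 0 | 2.5% |
| 0.2 | 1.095 | 18.4% | 1.897 | 46.7% |
| 0.3 | 1.643 | 35.5% | 2.846 | 80.4% |
| 0.5 | 2.739 | 75.4% | 4.743 | 99.7% |

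With 20% of lengths missing in one arm (n = 24), the three non-zero rows become 15%, 29% and 65%. In 20,000 simulated trials with n = 30, the rates at d = 0.3 and 0.5 were 36% and 75%, which agrees.

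**4. Between-arm comparison under the same drift.** With the drift equal in all arms and no device effect, a two-sample t test of 60 against 30 men rejected in 4.8% to 5.1% of 20,000 simulated trials for drifts of 0 to 0.8 SD (nominal 5%, two-sided). A drift common to the arms cancels.

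**5. Precision of the between-arm comparison.** Smallest detectable difference = (1.960 + 0.842) × √(1/n₁ + 1/n₂), in SD units, for two-sided 0.05 and 80% power (both assumed).

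| Lengths missing (assumed) | One traction arm v control | Both traction arms v control |
|---|---|---|
| 0% | 30 v 30: 0.72 | 60 v 30: 0.63 |
| 20% | 24 v 24: 0.81 | 48 v 24: 0.70 |
| 30% | 21 v 21: 0.87 | 42 v 21: 0.75 |

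**6. Effect of catch-up by controls.** Take an assumed early effect of 0.8 SD and no missing lengths. If controls make up 0, 25, 50 or 75% of it by month 9, the remaining difference is 0.8, 0.6, 0.4 or 0.2 SD. Power is then 87, 64, 34 or 12% (30 v 30) and 95, 77, 43 or 14% (60 v 30). At full catch-up no difference remains to detect.

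**The case against.** The strongest objection is that the added comparison does not answer the restoring question either. From month 6 every arm may use the device, so the 9-month contrast sets early traction plus optional use against no early traction plus optional use. If late traction fully restored length in controls, the arms would converge and success would look like a null result. This stands. A reader might infer that the randomised arms offer a controlled test of restoration. They do not: catch-up could be device effect or natural recovery, and no concurrent untreated group tells them apart. The comparison is an addition that answers a different question, persistence.

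A second tempting reading is that the before-after analysis is confined to men who chose to use the device. No section says so. All subjects enter the phase, the analysis set is not defined, and the first analysis in section 5.2 includes everyone regardless of compliance. It is the use that is self-selected, not demonstrably the analysis set.

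Third, this is one secondary objective of nine. The primary objective is a comparison with untreated controls, and the plan says that it will compare lengths, not that it will claim restoration. This bears on weight. It does not remove the gap, because section 1.1 states restoring as the aim of the phase.

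Fourth, the documents describe loss of length after surgery and never natural regain. If natural loss continues after month 6, the bias runs against the device. That is correct, and it is why the figures illustrate a range and do not predict an error rate.

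Finally, the added comparison is not automatically free of bias. Under section 3.5, men who cannot travel return questionnaires and diary by post, so their lengths will be missing, possibly unequally by arm.

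**Conclusion.** The point holds in a limited form. The length analyses named for the open-label phase are uncontrolled, and they cannot on their own support the restoring aim. With no device effect, assumed natural gains of 0.2 to 0.5 SD of the change would yield a significant gain in about 18% to 75% of trials with 30 men and 47% to 99.7% with 90, against a nominal 2.5%. These figures assume the drift, its direction and complete data, none of which the documents give. Natural loss would mask a benefit instead.

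The documents do not support going further and saying that the analysis is limited to users, or that the randomised contrast at 9 months would establish restoration. No analysis available in this design isolates restoration, which is itself a reason not to claim it from a before-after change. As a secondary objective with a wording-level remedy, this is a change that should be made, but it does not undermine the primary comparison.

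**What to change.** In section 5.2:

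1. Add a comparison of 9-month length by randomised arm, in all randomised men regardless of open-label use, adjusted for baseline length and randomisation stratum. Label it early versus delayed or optional access (does a 6-month difference persist?), not a test of restoration.
2. State how missing 9-month lengths will be handled, in particular for men followed by post.
3. Label the 6-to-9-month change, and its relation to use, as descriptive, with no efficacy claim for restoration from it alone. Define the set of men included. Bring the restoring aim in section 1.1 into line.
4. Reconcile the length of the open-label phase. Section 1.2 gives 6 months; the Study Summary and sections 1.5 and 3.5 give 3 months. This decides whether the 9-month visit falls at the end of the phase.

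The cost is SAP wording and one more model. No visit or measurement is added, because length at 9 months is already scheduled in every arm. The downsides are limited precision (about 0.63 to 0.87 SD detectable at 80% power with 0 to 30% missing, assumed), lower power still if controls catch up, and a weaker claim about restoration.

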2.1 Primary Objective

1. The primary objective is to assess penile length pre and post completion of RestoreX® traction therapy compared to control groups (no treatment) of subjects who have undergone a prostatectomy.

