3.6 Randomization Protocol

Following enrollment and completion of the initial length assessment, patients will be categorized into the appropriate strata based on their baseline stretched penile length; strata categorized as <10 cm, 10cm-13cm, 13.1cm-16cm, >16cm stretched length. Each stratum will have a separate randomization table provided such that one of three possible outcomes will occur no less frequently than every other case. This is done to better account for baseline variables that may impact outcomes and to assist with matching groupings appropriately.

The explanation of which grouping the patient is assigned will then be reviewed, and if the patient subject is assigned to the treatment group, a RestoreX® device will be provided.

4 Study Procedures

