4.2 Baseline Assessment

- Participant consented (if they were not originally consented at the pre-operative appointment)
- Obtained prior to randomization at time of catheter removal (part of standard care)

- Objective assessments
 - Penile length – measured from pubic symphysis to glanular corona
- Subjective questionnaires (attached)
 - Disease specific history
 - IIEF-15 (for patients who have not completed pre-operatively)
- Device usage diary provided for treatment group

4.3 6 Month Visit

- Penile length assessment
- Questionnaires (attached)
 - 6 month
 - IIEF-15
- Device usage diary retrieved from treatment group
- Device usage diary given to all participants (enter open label phase)

4.4 9 Month Visit

- Penile length assessment
- Questionnaire
 - 9 month
 - IIEF-15
- Retrieve device usage diary

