4.5 Assessment of Length

Penile length measurements will be obtained by a member of the clinical team using a measurement from the pubic symphysis to the corona of the glans penis. Measurements will be obtained post-operatively (after catheter removal) and at the 6 and 9 month follow-ups.

See **Attachments – Device Usage Diary, Disease Specific History, IIEF-15, Questionnaire 6 Month and 9 Month**

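### The primary length carries conflicting labels and no stated stretch method at any visit, so measurement technique can vary between visits

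*Combined protocol and SAP*

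**What the plan says.** The Study Summary (Statistical Methodology) describes the main comparison: "Statistical comparisons will be made comparing total penile length prior to and following therapy". The primary objective in Section 2.1 is to "assess penile length pre and post completion of RestoreX® traction therapy", with no qualifier on length.

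Section 3.6 acts once the initial length assessment is complete: "patients will be categorized into the appropriate strata based on their baseline stretched penile length". Section 5.2 also groups patients by baseline stretched length, then normalizes all data to a stretched length described as pre-operative.

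The measurement itself appears in two places. Section 4.2 has "Penile length – measured from pubic symphysis to glanular corona". Section 4.5 says the length is "obtained by a member of the clinical team using a measurement from the pubic symphysis to the corona of the glans penis", and on timing: "Measurements will be obtained post-operatively (after catheter removal) and at the 6 and 9 month follow-ups". Neither section mentions stretch. Neither gives a position, a stretch technique, a number of readings, a same-assessor requirement or blinding.

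**The concern.** Length is the only primary outcome, and it is analysed as a change between readings taken months apart. Such a change is interpretable only if both readings are the same quantity taken in the same way. Here the name of the quantity differs between sections, and the one method section is too thin to hold technique constant. Even if every reading is stretched, its value depends on how hard the assessor pulls, and nothing keeps the assessor the same.

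The stakes differ by comparison:

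- **Traction versus control.** A shift in technique equal across arms drops out of the difference in means but widens its standard error. A shift that differs by arm is bias. That is possible because control is no treatment, without a sham, and Section 3.5 asks patients to bring the device to the 6-month visit. The measurer may therefore know the arm.
- **Within-patient change (Section 5.2) and the open-label comparison of 9 months with baseline and with the start of that phase (Study Summary).** These have no concurrent untreated group, so an average shift in technique goes straight into the estimate.

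**Working it through.** **1. The labels side by side**

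| Place | Quantity | Stretch stated? |
|---|---|---|
| Study Summary | total length | no |
| 2.1 | length | no |
| 3.6 | baseline length | yes |
| 4.2 (baseline) | symphysis to corona | no |
| 4.5 (baseline, 6 and 9 months) | symphysis to corona | no |
| 5.2, grouping | baseline length | yes |
| 5.2, normalization | pre-operative length | yes |

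Two conflicts follow. Total length does not fit a corona endpoint, which omits the glans. A pre-operative length does not fit the schedule: Section 4.1 lists no length measurement, and Table 1 and Section 4.5 place the first one after surgery.

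**2. The plan's own figure**

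3 arms x 30 = 90, which agrees with Section 3.4. No alpha, power, effect size or SD is given, so no power calculation can be reproduced. For scale, at two-sided 0.05 and 80% power, 30 versus 30 detects (1.96 + 0.84) x sqrt(1/30 + 1/30) = 0.72 SD of change.

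**3. Effect of averaging readings (illustration)**

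Assumed inputs, none from the documents: reading-error SD s = 0.3 to 1.0 cm; true-change SD T = 1.0 to 1.5 cm; k independent readings averaged at each visit.

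Variance of change = T² + 2s²/k

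| T | s | k = 1 | k = 3 | Reduction |
|---|---|---|---|---|
| 1.0 | 0.3 | 1.18 | 1.06 | 10% |
| 1.0 | 0.5 | 1.50 | 1.17 | 22% |
| 1.0 | 1.0 | 3.00 | 1.67 | 44% |
| 1.5 | 0.3 | 2.43 | 2.31 | 5% |
| 1.5 | 0.5 | 2.75 | 2.42 | 12% |
| 1.5 | 1.0 | 4.25 | 2.92 | 31% |

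The saving is 2s² - 2s²/3 = (4/3)s². If a fraction c of the error variance is common to all readings within a visit (the same pull by the same person that day), the saving becomes (1 - c)(4/3)s². The table is therefore an upper bound.

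Power for an assumed 1.0 cm difference, 30 versus 30, two-sided 0.05, with one reading and then three:

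- T = 1.0: 94.6% to 96.4% (s = 0.3); 88.5% to 94.8% (s = 0.5); 60.9% to 85.1% (s = 1.0).
- T = 1.5: 70.0% to 72.2% (s = 0.3); 46.8% to 62.1% (s = 1.0).

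**4. If some follow-up readings were unstretched (illustration)**

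Suppose a share p of follow-up readings is d cm shorter for that reason. Mean change moves by p x d, and the variance rises by p(1 - p)d². With assumed p = 10-25% and d = 1-3 cm:

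- The shift runs from 0.10 x 1 = 0.10 cm to 0.25 x 3 = 0.75 cm.
- With T = 1.0 and no other error, the SD of change rises from 1.00 to between sqrt(1 + 0.09) = 1.04 and sqrt(1 + 1.6875) = 1.64 cm. Power for a 1.0 cm difference falls from 97.2% to between 96.0% and 65.6%.

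If p and d are equal in all arms, the shift cancels between arms and only the loss of power remains. It does not cancel in the within-patient or open-label comparisons.

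**The case against.** The strongest defence is that the plan, read as a whole, implies a single quantity. Section 3.6 stratifies straight after the initial length assessment on a stretched value, so that assessment is most naturally the stretched one. Section 4.5 then applies one method to all three visits, at a single centre. This largely stands, and it disposes of several stronger readings:

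- A reader might infer that the plan takes a stretched length at baseline and an unstretched one at follow-up. It does not say so. Stretch is unstated at baseline in Sections 4.2 and 4.5 just as it is at 6 and 9 months. The text permits a switch through under-specification; it does not prescribe one.
- A reader might infer one reading taken by anyone available. Section 4.5 names a member of the clinical team and is silent on the number of readings. Its wording describes the landmarks, not a count.
- A reader might infer that a change of technique would show up as lost length in the primary result. Section 2.1 compares with controls, so a change equal across arms cancels in the mean difference.

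It is also fair to say that replicate readings and a fixed assessor are good practice, and that their absence is not a contradiction. The attached forms are not available here and might hold measurement detail. Section 4.1 does not itemize its disease-specific variables.

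None of this reconciles total length with a corona endpoint, or a pre-operative normalizer with a schedule whose first length is post-operative. Nor does it supply a stretch method.

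**Conclusion.** The point holds as a labelling conflict combined with an under-specified method for the sole primary outcome. Total length including the glans is never measured under the stated method. Technique can vary between visits because nothing in the text fixes it.

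The consequence for the randomized comparison is extra noise if the variation is equal across arms, and bias only if it differs by arm. The within-patient and open-label comparisons can be biased either way.

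The size cannot be derived from the documents. Under the assumed SDs, averaging three readings cuts the variance of change by about 5-44%. The upper end needs a reading error as large as the true-change SD and errors that are independent within a visit. At reading-error SD 0.3 cm the power gain is only about 2 points. The direction is secure; the amount is not. The change is worth making because it is cheap, not because a large loss has been shown.

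**What to change.** - **Study Summary and Sections 4.2 to 4.5:** define the outcome once as stretched length from pubic symphysis to corona, with the same position and stretch method at baseline, 6 and 9 months. Replace the reference to total length in the summary.
- **Section 4.5:** take three readings at each visit, re-stretching between them, and analyse the mean. Use the same existing team member for a man's visits where possible, and record who measured. Averaging does not remove error that is constant for one assessor; keeping the assessor the same lets that part cancel in the change.
- **Section 5.2:** normalize to the post-operative baseline length, so that the text matches Section 4.5 and Table 1.

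The cost is wording plus two further readings if one is now taken, about a minute more per visit. It needs no added visit, staff or patients.
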